2.7 Evidence for viral load as a predictor of infectiousness

Mathematical modelling in human immunodeficiency virus (HIV) and herpesviruses and now COVID-19 suggests a significant percentage of transmission occurs from high peak VL which in all these diseases is during the asymptomatic period. Models by Josh Schiffer and Ashish Goyal suggest that a person has a 50% chance of infection with exposure to 10^7 SARS-CoV-2 RNA and <5% chance of infection with exposure to 10^5 SARS-CoV-2 RNA (Figure 2-5) (21). The model by Goyal et al (21) suggests that vaccine reduction in peak VL may reduce infectiousness. A 0.6 log reduction corresponds to ~50% VE_I and a 2.5 log reduction to ~90% VE_I (Figure 2-6). This suggests collecting nasal swabs every other day would be required to measure the vaccine effect on peak VL and area under the VL curve. Asymptomatic and pre-symptomatic cases of SARS-CoV-2 appear to play an important role in the onward transmission of the virus.

[figure not shown]

Figure 2-5 SARS-CoV-2 transmission probability as a function of shedding. A. Optimal infectious dose (ID) response curve (infection risk = P_t) and transmission dose (TD) response curve (transmission risk = $P_t * P_t$) curves for SARS-CoV-2. Transmission probability is a product of two probabilities, contagiousness and infectiousness. B-D. Three simulated viral shedding curves. Heat maps represent risk of transmission at each shedding timepoint given an exposed contact with an uninfected person at that time.

[figure not shown]

Figure 2-6 Vaccine efficacy against infectiousness versus the change in peak viral load.
Model by Goyal et al (personal communication).

2.8 Evidence for viral load as a marker of COVID-19 disease severity and clinical course

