Following completion of all procedures in the preceding list, and if results indicate that vaccination may proceed, vaccination is prepared and administered, per Moderna EUA Fact Sheet and Full Prescribing Information for Vaccination Providers that can be accessed at <https://www.modernatx.com/covid19vaccine-eua/>).

- End of study questionnaire at Month 5 (Visit 6)

For participants who have already received COVID-19 vaccination outside of study prior to Month 4 (Visit 5) visit or who decline vaccination, the following procedures are performed at Visit 5; Visit 6 will not occur (see [Appendix F](#)):

- Specimen collection
- End of Study questionnaire

9.7 Procedures for Main Cohort participant diagnosed with a SARS-CoV-2 infection during the study

If a participant is diagnosed with a SARS-CoV-2 infection during the course of the study, CDC guidelines on administration of vaccination will be followed.

Main Cohort participants who are clinically diagnosed with SARS-CoV-2 infection (from any test result indicative of acute infection) are referred to as clinically diagnosed index cases. They will be instructed to isolate per local guidelines and the following procedures will be performed:

- eDiary collection of daily symptoms of COVID-19 and assessment of whether clinical care was sought or hospitalization occurred (via self-report and/or request for medical records) through an eDiary for a period of 14 days or until symptoms have resolved, whichever is longer
- Daily nasal swabbing continued per schedule of procedures (see [Appendix E](#))
- Blood collection by phlebotomist or participant for SARS-CoV-2 clinical serology
- Close contacts identification (see Section [9.9](#))

Following resolution of the isolation period, participants will continue scheduled study visits. Follow-up duration for participants diagnosed with moderate or severe COVID-19 disease may be adjusted in consultation with the CRS (eg, to avoid interference with participant initiation of SARS-CoV-2 treatment).

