Appendix E Procedures for Main Cohort, Immediate Vaccination Group

Visit:	01 ¹	02 ²	03	04	05	06
Day:		D1	D29	D57	D113	D141
Week:		W0	W4	W8	W16	W20
Month:		M0	M1	M2	M4	M5
Procedure	Scr.	VAC1	VAC2			
Study procedures						
Screening consent (if used)	✓	—	—	—	—	—
Assessment of understanding	✓	—	—	—	—	—
Protocol consent (eConsent)	✓	—	—	—	—	—
Medical history questionnaire ³	✓	✓	—	—	—	—
SARS-CoV-2 infection risk assessment ³	✓		Weekly			
COVID-19 symptom surveillance ³	—		Weekly starts at week 2, not during week 5			
Confirm eligibility	✓	—	—	—	—	—
Obtain demographics ³	✓	—	—	—	—	—
Randomize	—	✓	—	—	—	—
SARS-CoV-2 testing questionnaire ³	—		approximately 2x per week			
End of study questionnaire ³	—	—	—	—	✓	—
Research Samples⁴						
Serum for Immunogenicity Assays and Storage	—	✓	—	✓	—	—
Serum for SARS-CoV-2 clinical serology ⁵	—	✓ ⁶	—	✓ ⁶	✓	—
Nasal swab	—		Daily ⁷			
Vaccination procedures						
COVID-19 symptom check ⁸	—	✓	✓	—	—	—
Vaccination	—	✓	✓	—	—	—

Greyed out visit column does not apply to this group.

1 Screening may occur over the course of several contacts/visits up to and including day 1, prior to vaccination.

2 Blood draws required at vaccination visits must be performed prior to vaccination.

3 Results from screening at school, if applicable, or at other locations will be captured via eDiary, please see Section 9.16.

4 From screening to the final study visit, the total blood volume to be collected from each participant will be approximately 40 mL (maximum) with a maximum of approximately 17 mL collected in a single visit.

5 For blood self-collected by a participant the maximum volume will be less than 1 mL in a single collection.

6 SARS-CoV-2 clinical serology testing may be performed on leftover blood from samples collected for immunogenicity assays. No separate blood sample is needed. If a Main cohort participant is also in the Prospective Close Contact (PCC) cohort related to

an index case or in the Case-ascertained Close Contact (CACC) cohort, one additional blood collection (self-collection) will be performed (see table below).

7 Daily swabs will be collected from vaccination through D113. Swabs will be returned via drop-off location(s) specified by the clinic or through the mail.

8 COVID-19 Symptom Check to be performed within 24 hours prior to vaccination.

The following **additional** procedures will occur for Main cohort, immediate vaccination participants, who fall under any of the following categories:

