3.2.6 SARS-CoV-2 exposure

Given the open-label nature of the study, it is possible that individuals in the Immediate Vaccination, SoC, and Vaccine Declined groups have different exposure to SARS-CoV-2. While the randomized groups are ensured to balance with respect to baseline factors, individuals in the Vaccine Declined Group are likely to differ from those in the randomized groups based on both baseline and time-varying factors related to exposure. Imbalanced exposure between groups may lead to bias in analyses that compare endpoint distributions between groups. A series of analyses will explore predictors of SARS-CoV-2 exposure based on baseline SARS-CoV-2 negative participants in the SoC group. Separate but identical analyses will explore predictors of exposure in the Vaccine Declined group.

The outcome of interest will be time to incident infection. Calendar time will be the time scale and participants will be censored using 'outside testing censoring'. Baseline and time-varying variables listed above in Section 3.2.5 will be screened univariately for their associations with SARS-CoV-2 infection based on Cox proportional hazards models that stratify on study site. Variables with p-values less than 0.10 will be retained. Retained baseline variables will be screened further to remove highly correlated variables; for pairs with absolute value of Spearman correlation > 0.90 , a randomly chosen member of the pair will be retained. Cox regression with lasso penalty, stratified on study site and implemented with glmnet and with the retained variables from the previous step, will be used to derive a 'risk score' that is used for

adjustment in multiple analyses described below. The linear predictor of the penalized Cox model will be used as the risk score. This risk score will be included as a covariate in efficacy analyses described in Section 7.

3.2.7 *Noncompliance with swabbing*

Noncompliance with daily nasal swabbing may result in missed endpoints and incompletely observed viral load trajectories.

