Alluvial plots will be used to explore noncompliance over study and calendar time, by enrollment group and study site and other baseline covariates. Descriptive tables will summarize noncompliance over study time by enrollment group. Compliance will be defined in two ways, with swabs expected starting from either 1. enrollment date or 2. first swab date (or enrollment date if participant had no swabs). Days with a swab will be expected until minimum of the day before the date CRF-confirmed study completion, 111 days after enrollment and the last expected swabbing date (Dec. 31, 2021). Additionally, swabs will not be expected after outside vaccination

or termination. Time (weeks) after these two events (outside vaccination and termination) will be displayed separately in the plots. Compliance metric for participant weeks with at least one expected swab day will be the % (of expected) days with a swab, categorized as 0%, 1-29%, 30-58% and 59-100% (these categories will be labelled as 0, 1-2, 3-4 and 5-7, respectively, corresponding to a week with 7 expected swab days).

A GEE model will be used to explore predictors of time-varying non-compliance. Baseline and time-varying covariates listed in 3.2.5 will be considered for inclusion in the model. Participants will be censored at the earliest of outside vaccination or study termination.

If predictors of non-compliance, other than enrollment group, study time, calendar time, and covariates associated with outside vaccination (Section 3.2.5) or exposure risk (Section 3.2.6) are identified, these will be accounted for in efficacy analyses described in Section 7 through covariate adjustment or IPCW.

3.2.8 *Blood sample exclusions*

Prior to deriving the baseline serostatus and the seroconversion event, the following blood sample data will be excluded to account for replacements or problematic samples:

- Original insufficient in-clinic samples when replacement samples were collected for the same visit (see Section 8 of the Phlebotomy Specimen Collection Study Specific Procedures)
- Self-collected (TASSO) samples resulted as “Test Not Performed” by the lab (due to various reasons, e.g. insufficient/incorrect/damaged/expired/unused sample, processing error)
- In-clinic samples with more than 90 days between blood draw and lab processing
- TASSO samples with more than 7 days between blood draw and lab receipt

3.2.9 *Nasal swab record exclusions*

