7.3 To evaluate the vaccine effect on SARS-CoV-2 viral load

Given the early termination, the study is underpowered to look at the vaccine effect on viral load. Therefore a limited, descriptive analysis will be performed. Descriptive statistics for peak viral loads on the cycle threshold (CT) scale among FAS-P acquisitions (censored at outside vaccination) will be tabulated by lab (Corteva vs. UW/Northwell), target (N1 and N2) and arm. Peak viral load will be defined as the minimum observed CT per participant, lab and target. Participants with CT data from both labs will be excluded. Descriptive statistics will include N, mean, minimum, median, quartiles and median. Results are stratified by lab to address potential differences between labs. We will also present the descriptive statistics for the number of days with a positive study PCR (qualitative) per participant among FAS-P acquisitions, broken down by arm.

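### SAP 7.3 summarises shedding by arm as a count of PCR-positive swab days, with no swab denominator and no censoring, so the figure mixes length of shedding with swab frequency and with the end of scheduled swabbing

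*SAP*

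**What the plan says.** SAP 7.3 states that the study is underpowered for viral load after early termination. "Therefore a limited, descriptive analysis will be performed". It has two parts. For peak, "Peak viral load will be defined as the minimum observed CT per participant, lab and target", tabulated by lab, target and arm. For shedding, it gives descriptive statistics for the "number of days with a positive study PCR (qualitative) per participant among FAS-P acquisitions", by arm. Neither part mentions the number of swabs taken, the spacing of swabs around the infection, or what to do when swabbing ended while the participant was still positive.

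SAP 2.2 still lists duration of shedding above the limit of detection under secondary objective 4. No other part of the SAP analyses it. Protocol 6.4.4 planned a duration estimated empirically or from a fitted curve, and a model-based peak as a secondary analysis. SAP 7.3 contains neither.

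On swabbing itself:

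- Protocol Appendix E, footnote 7: "Daily swabs will be collected from vaccination through D113". Appendix F sets the same last day for the other two groups.
- Protocol 9.7, after a diagnosis: "Daily nasal swabbing continued per schedule of procedures". It gives no extension beyond that schedule.
- SAP 3.2.7 sets the limits of expected swabbing for its compliance measure, including "111 days after enrollment and the last expected swabbing date (Dec. 31, 2021").
- SAP 3.2.7 also recognises the risk: "Noncompliance with daily nasal swabbing may result in missed endpoints and incompletely observed viral load trajectories".
- Protocol 2.7 says that "collecting nasal swabs every other day would be required to measure the vaccine effect on peak VL" and area under the curve.

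**The concern.** A count of positive days is a product of two things: how long the participant shed virus, and on what share of those days a swab was taken and resulted. Without a swab denominator the reader cannot separate them. Without censoring, an episode still positive at the last scheduled swab looks the same as one that cleared on that day.

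This matters because the table is split by arm under a heading about the vaccine effect on viral load. Protocol 2.11.2 says that open-label differences may include adherence to study procedures. Protocol 6.4.2 plans to compare compliance between arms, and 6.4.3.1 plans adjustment of the infection analysis if swabbing differs. SAP 3.2.7 allows covariate adjustment or censoring weights in the Section 7 efficacy analyses, but 7.3 specifies neither. An arm that swabs less often, or whose infections fall closer to the end of swabbing, would show fewer positive days with no biological difference. The reverse pattern could conceal a real one.

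**Working it through.** **1. The plan's own figure.** The documents give no figure for the positive-day count. The only viral load figure is the design power for peak: 96.9% for a 1-log10 reduction with 225 infections (75 vaccinated, 150 unvaccinated), SD 1.8, one-sided 0.025. SE = 1.8 × √(1/75 + 1/150) = 0.2546, and 1/0.2546 − 1.960 = 1.968, which gives 97.5% (97.4% with the t distribution). This reproduces the stated figure to within simulation error. It is not in question and serves below only as a yardstick.

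**2. Swab frequency and the positive-day count.** Assumptions, since the documents give no shedding curve: a 10-day episode, and each day swabbed independently with probability p = k/7 for k swabs a week. Let q = 1 − p. Only infections with at least one positive swab are counted.

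- Mean count = 10p / (1 − q^10).
- Mean first-to-last span = 10 − 2(F − 1), where F = 1/p − 10q^10/(1 − q^10) is the mean day of the first positive.

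Worked case, k = 1.5: p = 0.2143 and q^10 = 0.0897. Count = 2.143/0.9103 = 2.4. F = 4.667 − 0.897/0.9103 = 3.68, so span = 10 − 2 × 2.68 = 4.6.

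| Swabs a week | Mean positive-day count | Mean first-to-last span |
|---|---|---|
| 7 | 10.0 | 10.0 |
| 5 | 7.1 | 9.2 |
| 3.5 | 5.0 | 8.0 |
| 1.5 | 2.4 | 4.6 |

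The last two rows are the midpoints of the SAP's own 3–4 and 1–2 compliance bands. Within its single 5–7 band the count already falls by 29% (10.0 to 7.1). If one arm swabbed 7 times a week and the other 5, identical episodes would differ by 2.9 counted days, against 0.8 days of span.

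**3. End of swabbing.** If infections are spread evenly over D1–D113, the share cut off by D113 is about the shedding length divided by 113: 10/113 = 8.8% for 10 days, 14/113 = 12.4% for 14 days. The share is higher if infections cluster before the last swabbing date. In a simulated 12-day course with daily swabs, stopping 5 days after onset leaves 5.0 of 12.0 positive days.

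**4. Minimum CT.** This was simulated with an assumed triangular curve: mean 3 days up and 9 down, peak CT mean 22 and SD 4, limit CT 40, 3.32 cycles per log10. The observed minimum exceeds the true peak CT by 0.8 cycles at 7 swabs a week, 1.5 at 5, 2.0 at 4, 2.9 at 3 and 4.3 at 2. Across curves from 2 up/6 down to 4 up/12 down, going from 7 to 2 swabs a week moves it by 2.8 to 4.2 cycles. That is 0.85 to 1.26 log10, about the size of the 1-log effect in step 1. Stopping swabs 5 days after onset moves it by only about 0.1 cycle (0.93 against 0.81).

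**5. Equal swabbing in both arms.** Shortening the decline from 9 to 6 days and raising peak CT by 3 gives a positive-day ratio of 0.75, 0.75 and 0.78 at 7, 4 and 2 swabs a week. The minimum CT difference is 3.05, 3.15 and 2.99. The true values are 9/12 = 0.75 and 3. Both summaries still respond to the course of infection.

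**The case against.** The strongest reply is that 7.3 is openly limited, descriptive and underpowered. It plans no test, interval or effect estimate, and SAP 2.4 treats analyses of the randomized participants as post-hoc. The positive-day count is labelled literally and never called a duration. SAP 3.2.7 will show compliance over time by enrollment group, with plots and a model of noncompliance. This stands as a limit on the harm. It does not remove the problem: a by-arm table invites comparison, and the compliance outputs are not per infection.

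Several stronger readings are tempting and are not supported:

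- *The two summaries reflect swabbing instead of infection.* Step 5 contradicts this. Bias between arms needs unequal swabbing or timing.
- *The peak definition departs from the protocol.* Protocol 6.4.4 also estimates peak by the observed maximum. The every-other-day remark in Protocol 2.7 is background for the collection schedule and sets no inclusion rule for analysis.
- *Infections near the end of swabbing show a weaker peak.* Step 4 finds almost no shift unless swabbing stops before the peak.
- *Late starters enter mid-episode.* SAP 3.2.2 requires a prior negative PCR. It sets no maximum gap, so this protection is partial.
- *Outside vaccination ends swabbing.* SAP 3.2.7 only removes those days from a compliance denominator. Protocol 2.11.2 keeps such participants on the same procedures, and 9.11 encourages continued follow-up.

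The remedy also has limits. The span shortens when swabbing is very sparse. A densely swabbed subset is selected on behaviour after infection and drops the truncated episodes.

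**Conclusion.** The concern holds for the shedding summary. A raw count of positive swab days is close to proportional to swab frequency and treats episodes cut off by the schedule as complete. Under the 10-day assumption it runs from 10.0 down to 2.4 across plausible swab densities, while the first-to-last span runs from 10.0 to 4.6 and loses far less at 3.5 or more swabs a week. For peak the concern is narrower: minimum CT is fairly stable at 5 to 7 swabs a week, is lowered in apparent strength by sparse swabbing, and barely moves with truncation.

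These sizes rest on assumed shedding curves, independent daily swabbing and, for truncation, infections spread evenly over follow-up. None is an estimate of actual bias between arms. A reader might infer that the trial's shedding comparison is biased in a known direction. The documents do not support that, because they give no observed compliance by arm. No power or sample-size figure is affected.

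**What to change.** In SAP 7.3:

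1. Replace, or accompany, the positive-day count with time from first to last positive swab, right-censored at the last resulted swab when no later negative exists. Summarise it by Kaplan-Meier by arm.
2. Report by arm, per infection: number of swabs, gap from last negative to first positive, and days from first positive to last swab.
3. Keep minimum observed CT in all infections as the main peak table. Add infections swabbed at least every other day as a sensitivity table only, noting that this subset is smaller and selected on swabbing after infection.
4. State that the span still shortens when swabbing is very sparse.

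The cost is SAP wording and a few extra table rows from swab dates and results already held. No new data are needed.

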8. IMMUNOGENICITY ANALYSES

Immunogenicity analyses will be described in a separate 'Immune Correlates SAP'.

9. SECONDARY ENDPOINTS

9.1 To evaluate the impact of Moderna COVID-19 Vaccine on secondary transmission of SARS-CoV-2 infection, using data for the Prospective Close Contact (PCC) cohort and Case- Ascertained Close Contact (CACC) cohort (i.e., to evaluate vaccine efficacy against infectiousness or VEI)

Because there were inadequate number of contacts enrolled into this study, the analyses needed to complete this objective cannot be performed.

9.2 To evaluate the efficacy of Moderna COVID-19 Vaccine to against COVID-19 disease

Objective: To evaluate vaccine efficacy against COVID-19 disease, (i.e., to evaluate VED).

Outcome: PCR-confirmed COVID-19 diagnosis where symptomology on a given day as reported by e-diary (weekly or daily) occurs no more than 3 days prior to and no more than 14 days after the administration of the first nasal swab that is PCR positive. This represents a slight departure from the protocol that only relies on weekly testing to expand to also include daily symptom questionnaires that start after a positive test to increase precision of the disease definition.

Data sets:

Definition of Endpoint: COVID-19 is defined as symptomatic disease based on the following criteria as assessed in daily and weekly self-reported symptom logs, coincident with virologic confirmation (RNA PCR Ct < 40):

- at least one of the following signs/symptoms: hospitalization, fever, chills, cough, shortness of breath, difficulty breathing, tiredness/fatigue, muscle aches, joint aches, body aches, headache, change in sense of taste, change in sense of smell, sore throat, nasal congestion, runny nose, nausea, vomiting, diarrhea, oral ulcers (mouth sores) and clinical or radiographical evidence of pneumonia

This definition defers from the primary endpoint definitions in the phase 3 COVID vaccine trials (e.g. COV-19 3001) and the protocol because some symptoms were not collected (thromboembolic event, myocardial infarction, myocarditis, chilblains, or multi-inflammatory syndrome) and symptom diaries for some participants were incomplete and/or not collected during the specified time interval.

Symptom onset date will be defined as the first symptomatic day according to the daily or the weekly symptom log that is in the interval starting no more than 3 days prior to and no more than 14 days after the first positive nasal swab. We will assume symptomatic logs represent symptom presence on the day of the log for the daily logs and in the period between a given log and the preceding log (or enrollment if no preceding log) for weekly logs. The latter assumption may be violated if participants experienced the symptom only for part of the period (cannot be determined from the log).

A participant will be defined as having reached the endpoint if they have the diagnosis above. The time of the endpoint will be the onset of symptoms. Participants who do not have the endpoint will be censored at the earlier of first positive PCR without symptoms (or with missing symptom logs) and outside vaccination censoring. As a supportive analysis, we will also consider censoring at the earlier of first positive PCR without symptoms and ITT censoring. Death and hospitalization with positive PCR will be counted in the endpoint.

Analysis Details:

A participant will be defined as having reached the endpoint if they have the diagnosis above. The time of the endpoint will be the onset of symptoms. Participants who do not have the endpoint will be censored at the last time they were known to be symptom- and infection-free. Death and hospitalization will be counted in the endpoint. Rate tables and VE estimation analogous to analyses of the acquisition endpoint will be produced. The same set of covariates will be adjusted for in VE estimation as for the acquisition endpoint.

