9.15 COVID-19 symptom surveillance for Main Cohort

Participants will be monitored for symptoms of COVID-19 throughout the course of the study via a weekly eDiary. These symptoms will be used to establish whether a participant meets criteria for COVID-19 disease as defined by Secondary Endpoint 4. If a participant has symptoms consistent with COVID-19, they will be encouraged to seek testing and clinical care through their local testing and care facilities. Results of testing will be reported through the eDiary and participants who have positive test results will follow procedures described in Section 9.7.

For Immediate Vaccination Group only: due to the overlap of symptoms that can result from vaccination and symptoms of COVID-19, monitoring will begin 7 days following the first study product administration. Symptom monitoring will be paused 7 days following the second product administration.

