2.2 Study Objectives and Endpoints

Primary Objectives	Primary Endpoints
1. To evaluate the efficacy of Moderna COVID-19 Vaccine against SARS-CoV-2 infection (i.e., to evaluate vaccine efficacy against infection or VES).	SARS-CoV-2 infection diagnosed by PCR among participants who were SARS-CoV-2 seronegative at enrollment
2. To evaluate the effect of Moderna COVID-19 Vaccine on peak nasal viral load as a measure of infection and a proxy of infectiousness	Peak viral load in nasal samples from participants diagnosed with SARS-CoV-2 infection among participants who were SARS-CoV-2 seronegative at enrollment
Secondary Objectives	Secondary Endpoints

1. To evaluate the impact of Moderna COVID-19 vaccine on secondary transmission of SARS-CoV-2 infection, using data for the Prospective Close Contact (PCC) cohort and Case-Ascertained Close Contact (CACC) cohort (ie, to evaluate vaccine efficacy against infectiousness or VEI)
	
Number of adjudicated* secondary transmission events in PCC and CACC cohorts from main study participants who were SARS-CoV-2 seronegative at enrollment.
 
*based on questionnaire-based epidemiologic data, antibody and viral dynamics, and viral sequence data

2. To evaluate the efficacy of Moderna COVID-19 Vaccine to prevent serologically confirmed SARS-CoV-2 infection
	
SARS-CoV-2 antibodies to the nucleocapsid protein post visit 3 (month 1), among participants who were SARS-CoV-2 seronegative at enrollment

3. To evaluate vaccine efficacy against COVID-19 disease, (ie, to evaluate VED) using weekly e-diaries and confirmatory PCR testing
	
SARS-CoV-2 infection confirmed by PCR among participants who were SARS-CoV-2 seronegative at enrollment, coincident with the following symptoms:
 
 • at least TWO of the following systemic symptoms: Fever ($\geq 38^{\circ}\text{C}$), chills, myalgia, headache, sore throat, 
OR
 
at least ONE of the following signs/symptoms: cough, shortness of breath or difficulty breathing, new olfactory or taste disorder, clinical or radiographical evidence of pneumonia, thromboembolic event, myocardial infarction, myocarditis, chilblains, or multi-inflammatory syndrome

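### The COVID-19 disease endpoint back-fills weekly symptom logs with no limit on the gap and accepts any one symptom, with no analysis under the protocol's own symptom rule

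*SAP*

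**What the plan says.** **Window and look-back (SAP 9.2).** Infection counts as disease if symptomology "occurs no more than 3 days prior to and no more than 14 days after the administration of the first nasal swab"; the swab meant is the earliest one with a positive PCR result. A daily log speaks for its own day. A symptomatic weekly log speaks for every day "in the period between a given log and the preceding log (or enrollment if no preceding log) for weekly logs". Onset is the first symptomatic day inside the window. The section concedes that a symptom may have lasted only part of the period. It gives no limit on the gap and no rule for a daily log that disagrees with a back-filled weekly one.

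**Completeness (SAP 9.2).** "symptom diaries for some participants were incomplete and/or not collected during the specified time interval".

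**Symptom rule.** SAP 9.2 requires "at least one of the following signs/symptoms: hospitalization, fever, chills, cough, shortness of breath, difficulty breathing, tiredness/fatigue", and the list goes on to headache, congestion, runny nose, nausea and diarrhea, among others. SAP 2.2, like Protocol Section 3, requires "at least TWO of the following systemic symptoms", or one sign from a second list that includes cough, breathing difficulty and a taste or smell disorder. SAP 9.2 discloses the departure and gives two reasons: some rare items were not collected, and some diaries were incomplete or mistimed.

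**Planned pauses.** For the Immediate arm only, Protocol 9.15 says "monitoring will begin 7 days following the first study product administration", because vaccine reactions overlap with COVID-19 symptoms. Appendix E starts that arm's weekly logs in week 2 and omits week 5. Appendix F shows no pause for the other two groups.

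**Censoring (SAP 9.2).** One paragraph censors at the earlier of a first positive PCR without symptoms (or with missing logs) and outside-vaccination censoring. The next says: "Participants who do not have the endpoint will be censored at the last time they were known to be symptom- and infection-free".

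**The concern.** There are three separate problems.

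1. Without a cap, a log filed after a long gap can place a symptom in the window that occurred well outside it. Because onset is the first symptomatic day in the window, such a log tends to set onset at day -3. VE_D is to be estimated as for the acquisition endpoint, whose model in SAP 7.2 changes the hazard at each dose. An event dated too early can therefore be charged to the wrong dose period.
2. The look-back undoes, in one arm of an open-label trial, the protocol's exclusion of the reactogenicity weeks.
3. The symptom rule is looser than the stated endpoint, and the only supportive analysis of this endpoint changes the censoring. Nothing planned would show how far VE_D depends on the rule.

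At stake is whether the reported VE_D answers the objective in SAP 2.2 or drifts towards VE_S.

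**Working it through.** The documents give no event count, power or misclassification rate for the disease endpoint, so there is no stated figure to reproduce.

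**Reach of the back-fill.** The window of -3 to +14 is 18 days inclusive. A log period of g days touches it if the log is filed by day 13 + g. Averaged over log timing, the periods that touch the window cover 18 + g - 1 days.

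| Gap g | Latest log that can count | Days covered |
|---|---|---|
| 7 | day +20 | 24 |
| 14 | day +27 | 31 |
| 28 | day +41 | 45 |

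**Where the post-dose weeks matter.** Take dose 1 on day 1 and dose 2 on day 29. Days 1-7 fall in the window for a first positive swab up to day 10 (7 + 3). Days 29-35 fall in it for a first positive swab from day 15 (29 - 14) to day 38 (35 + 3). The first Immediate-arm log has no predecessor, so it reaches back to enrollment across week 1. The first log after the second pause reaches back across week 5.

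**Effect of a less specific rule.** Let p0 and p1 be the true symptomatic shares of unvaccinated and vaccinated infections, and f the chance that an infection without COVID-19 symptoms is counted as disease. Then p1 = p0(1 - VE_D)/(1 - VE_S), and with equal f in both arms

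observed VE_D = 1 - (1 - VE_S) × [p1 + (1 - p1)f] / [p0 + (1 - p0)f].

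Inputs: VE_S 50% (SAP 2.5); p0 = 0.60, from the 40% asymptomatic figure in Protocol 2.6. The weekly chance q of an unrelated listed symptom is not in the documents and is assumed.

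*Symptom rule, no back-fill, true VE_D 80% (assumed).* Per 100 unvaccinated infections there are 60 symptomatic and 40 not. The matching 50 vaccinated infections split 12 and 38. f = 1 - (1 - q)^(18/7).

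- One symptom, q = 5%: f = 0.124; VE_D = 1 - (12 + 38 × 0.124)/(60 + 40 × 0.124) = 74.3%.
- Stricter rule, q = 2% (assumed): f = 0.051; VE_D = 77.6%.
- One symptom, q = 10% and 20%: 69.8% and 63.1%.

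The difference between the two rules at the first pair of rates is about 3 points.

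*Back-fill, true VE_D 90% (the value in the modelling example in Protocol 2.3), p1 = 0.12.* f = 1 - (1 - q)^((17 + g)/7). At q = 5%:

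| Look-back | f | Observed VE_D |
|---|---|---|
| none | 0.124 | 82.4% |
| 7-day gaps | 0.161 | 80.3% |
| 14-day gaps | 0.203 | 78.1% |
| 28-day gaps | 0.281 | 74.2% |

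Back-fill costs 82.4 - 80.3 = 2.1 points with weekly logs and 82.4 - 74.2 = 8.2 with 28-day gaps. At q = 1% the 7-, 14- and 28-day figures are 87.8, 87.2 and 86.0%; at q = 10% they are 73.2, 70.1 and 65.3%.

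*Unequal gaps.* With 14-day gaps in the Immediate arm only and 7-day gaps in the other, q = 5% gives 77.5% instead of 80.3%. This applies the longer gap to every Immediate-arm infection, so it overstates the effect of two pauses alone; it also leaves out any reaction symptoms. The bias turns upward only if f in the vaccine arm is below p1(1 - p0)/[p0(1 - p1)] = 0.091 of f in the control arm.

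**Censoring.** For an infection without symptoms, the first rule stops the clock at the first positive swab and the second at the last time known to be clear. The dates differ mainly by the interval from last negative to first positive swab. The second rule does not mention outside vaccination.

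**The case against.** The case for the SAP has several parts that stand.

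- Incomplete diaries are a plausible reason for not insisting on two recorded symptoms. They do not explain adding items outside the protocol list, or planning no analysis under the protocol rule.
- Protocol 9.7 schedules daily symptom tracking for at least 14 days after diagnosis, and SAP 9.2 brings those logs in. Good daily logs cover much of the window, but the appendices count their days from notification, so earlier days rest on weekly logs.
- A PCR-positive person with fatigue or a runny nose may have mild COVID-19. Counting that person is partly a disclosed broadening of the endpoint, not pure misclassification.
- The protocol rule also has background positives, which is why the comparison above is with 78% and not 80%.
- This is a secondary endpoint in a stopped trial, and SAP 2.4 treats the randomized analyses as post hoc.

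A reader might infer that asymptomatic infections in general become disease, or that VE_D collapses onto VE_S. The documents do not support that. An infection needs a symptomatic log whose period touches the window; those with no symptoms or missing logs are censored. Full convergence needs f = 1 in both arms. A reader might also take the 74, 70 and 63% figures as the cost of back-fill; they contain none. Nor do the documents establish the size of any difference between arms, since neither the actual log gaps nor the diary's recall wording is given.

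**Conclusion.** The point holds as a defect in the endpoint rules. The uncapped look-back, its reach into the excluded post-dose weeks in one arm, the two symptom definitions and the two censoring rules are all in the text. If true VE_D exceeds VE_S and misclassification is similar in the arms, the direction is towards VE_S. The size depends on a background symptom rate and log gaps that the documents do not give. Under the assumed rates the symptom rule costs about 3 points against a stricter rule, and back-fill about 2 to 8 points depending on the gap. These come from different assumed values of true VE_D and should not be added. Disclosure of the departure does not replace a sensitivity analysis, and VE_D estimation is retained. The change is worth making before the analysis, but the documents do not show that the result would be reversed.

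**What to change.** 1. Cap the look-back of a weekly log at 7 days in all groups, and let a daily log take precedence where both cover a day. The cap removes the effect of long gaps, not the roughly 2 points that remain with weekly logs.
2. Pre-specify a VE_D analysis under the SAP 2.2 symptom rule, restricted to collected items, and report it beside the any-one-symptom version. State how fever is handled, since 2.2 has a temperature threshold and the 9.2 list does not.
3. Add a sensitivity analysis that leaves out weekly-log symptoms attributed to the 7 days after a study dose. It should not be the main rule: it can also drop genuine cases in the Immediate arm while the same symptoms count in the Standard of Care arm, and so push VE_D upward.
4. Report the distribution of log gaps by arm.
5. Keep one censoring rule: the earlier of the first positive PCR without qualifying symptoms (or with missing logs) and outside-vaccination censoring.

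The cost is SAP wording and endpoint code, with no new data. The stricter rule will give fewer disease events and somewhat wider intervals; the documents do not allow the number to be estimated.
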